7.0 DATA AND SPECIMEN BANKING

7.1 Location of Data Storage. Data will be retained from this pilot feasibility study to inform the development and refinement of future versions of the adherence intervention. The Excel database containing identifiable information, connecting participants to their study ID number (see Section 17.3), will be deleted at the closure of the study. Databases including de-identified adherence (from CertiScan® cloud) and questionnaire (from REDCap) data will be stored in a password-protected electronic file on the CCHMC hard drive for 10 years after the study has been closed. Data from this study will be used to inform an R01 or U-series multi-site trial of an adherence promotion intervention. A 10 year period was selected to ensure that data informing the larger study (data from this study) are available to inform modifications throughout the potential R01 or U-award period. After the study has been closed, only the PI will have access to the data.

7.2 Procedures to Release Data.

De-identified data may be shared with other individuals according to procedures outlined in the Data Sharing Agreement linked to this protocol.

8.0 SHARING OF RESULTS WITH SUBJECTS

AYAs will receive feedback on their adherence as part of this study. If a provider suspects non-adherence and believes that reviewing adherence data in our study could help to inform their clinical care, we will share the relevant data with the participant's provider. Participants will consent to this data sharing during the consent process. The AYA may also share these data with their care providers if they choose. No other individual subject results will be shared with participants or others not involved in the conduct of this study.

A summary of study results will be provided to study participants via a newsletter.

9.0 STUDY TIMELINE

9.1 Subject Participation Duration

Adolescents and young adults enrolled in this study will participate in a 4-week run-in period, 1 week pre-treatment assessment, 8-week intervention or control group, and 4 week post-treatment period. In all, the estimated duration of subject participation is 17 weeks.

Given the demanding nature of cancer treatment, all study procedures can be completed +/- 2 weeks of the planned completion date and still be considered completed "on time."

9.2 Enrollment Duration

Based on the number of eligible AYAs receiving care at the 3 participating institutions, it is estimated that participant enrollment will be completed in 12 months.

9.3 Study Timeline

The Notice of Award was issued on December 12, 2022. The proposed study timeline is detailed in Table 4.

Table 4. Study Timeline	
Dates	Tasks
December 2022 to February 2023	Prepare study materials and train study staff
February 2023 to November 2024	Participant enrollment
January 2023 to March 2025	Data collection
July 2023 to December 2026	Data analysis, cleaning, and publication

10.0 INCLUSION AND EXCLUSION CRITERIA

10.1 Eligibility Screening and Criteria

This study includes a 4 week run-in period during which eligibility will be determined. First, AYAs deemed eligible per inclusion and exclusion criteria 1-7 (Table 5) will be identified by a member of the study team via electronic medical record review. A waiver of HIPAA authorization is requested for preparatory research to identify potential participants based on inclusion/exclusion criteria. AYAs deemed eligible per criteria 1-7 and interested in participating will then complete the consent process as per Sections 13 and 22.

Table 5. Inclusion and Exclusion Criteria and Rationale

Inclusion Criteria (Rationale)

1. Patient between 15 and 24 years of age at consent visit (unique biological characteristics and behavioral transitions)
2. Patient diagnosis of cancer (intervention designed to address medical components of oncology treatment)
3. Patient prescribed oral prophylaxis or chemotherapy (non-adherence to these medications is linked to relapse & death)

Exclusion Criteria (Rationale)

4. Patient is not fluent in English (piloting an intervention to be delivered in multiple languages is beyond the scope of this study)
5. Patient evidences significant cognitive deficits per medical team (may interfere with intervention comprehension and/or participation)
6. Patient's medical status/condition precludes participation per medical team, patient, or caregiver (ensuring ethical recruitment)
7. Patient enrolled on a medical trial requiring medication storage in a trial-provided container (adherence measured via electronic monitor)
8. *Patient demonstrates ≥ 95% adherence⁹ during run-in (maximize accuracy of evaluation of preliminary efficacy)**
9. *Patient declines to use or has difficulty using the electronic monitoring device (minimize missing data)**

**determined during run-in period*

Prescribed Oral Medication Regimen Eligibility Criteria: An AYA's oral medication regimen can be modified based on their treatment response and thus it is possible that some enrolled AYAs will discontinue their medication prior to the end of the 17 week study. To minimize the likelihood of enrolling these patients, we will consult with an oncologist prior to enrolling each patient and only enroll patients who the medical team believes (at the time of enrollment) will be prescribed an oral prophylactic or chemotherapy medication for the 17 week study duration.

Run-In Period to Confirm Eligibility: After an AYA is enrolled, they will receive an electronic monitoring device and be asked to store their eligible oral medication in this device for the duration of their participation in the study. These criteria will be confirmed during the 4-week run-in period as detailed in Section 6.2.a.

10.2 Inclusion of Vulnerable Populations

Teenagers ages 15-17 years of age are eligible to participate in this study.

As our population includes women of child-bearing age, pregnant women may be eligible to participate.

Adults unable to consent and prisoners are not eligible to participate.

11.0 VULNERABLE POPULATIONS

The cohort will consist of patients between the ages of 15 and 24 years at baseline. This is a minimal risk study, including risks no greater than those encountered in routine behavioral assessment and clinical care. The steps taken to minimize coercion or undue influence during the process of obtaining informed consent will be followed in accordance with all applicable regulatory requirements. A patient and their family will not be approached if they 1) do not meet the proposed study criteria; and/or 2) are under distress. Additional procedures for obtaining consent are listed below.

This is a minimal risk study with no risk to the fetus.

12.0 LOCAL NUMBER OF SUBJECTS

12.1 Total Number of Subjects to be Accrued Locally

Recruitment will be ended when 40 AYAs are randomized. It is estimated that approximately 15 AYAs will be recruited locally with the remainder recruited at collaborating sites.

12.2 Total Numbers Completing Each Phase of Study

There are likely to be AYAs who are deemed eligible per inclusion and exclusion criteria 1-7 but are deemed ineligible due to criteria 8-9 following the 4 week run-in period. It is also possible that some participants will not complete initial study procedures (i.e., no-show for pre-treatment assessment visit). As a result, additional AYAs (estimated $n = 10-20$ AYAs) will be enrolled until a total of 40 AYAs are randomized.

13.0 RECRUITMENT METHODS

Participants will be recruited from the Cancer and Blood Diseases Institute (CBDI) at CCHMC and collaborating sites (see title page). Participants deemed eligible per inclusion and exclusion criteria 1-7 will be identified via electronic medical record review. A member of the study team will review the electronic medical records of these patients and to determine AYA eligibility.

Eligible participants can be recruited either in-person or remotely.

13.1 In-Person Recruitment Procedures

Eligible participants may be approached by study personnel during a clinic appointment or inpatient admission to extend an invitation to participate in the study and verify inclusion/exclusion criteria. A recruitment script will be followed. A study flyer may be provided to interested participants.

Primary Site (CCHMC) Procedures. If the AYA is willing to participate, the study staff will obtain appropriate informed consent/assent and a signed HIPAA authorization form. No further attempts will be made to contact disinterested AYAs. This recruitment strategy has been successful for the PI's previous studies (79-94% enrollment).

Collaborating Site Procedures. For AYAs receiving care at collaborating sites, study staff at the collaborating site will be responsible for screening and approaching eligible patients. If the patient is interested in participating in the study, study staff at that site will obtain informed consent/assent, signed HIPAA authorization form, and contact information. This information will be securely emailed to CCHMC via a password-protected Excel sheet. The password-protected Excel sheet will be saved on a secure drive on CCHMC's network. Only study staff will have access to the Excel sheet. Of note, all staff at these sites will be trained in informed consent procedures by CCHMC study staff. No further attempts will be made to contact disinterested AYAs. This recruitment strategy has been successful for the PI's previous multi-site studies (91-95% enrollment).

13.2 Remote Recruitment Procedures

Patients may also be recruited remotely. Specifically, eligible participants may be mailed a letter and flyer describing the study procedures. The letter will include instructions regarding opt-out procedures (participants call or email a designated phone number/email address). Eligible participants who do not opt-out will be contacted by a member of the study team within approximately two weeks and consent procedures will be completed. This recruitment strategy has been previously used by the PI on multi-site studies of young adult cancer survivors (IRB # 2018-1885) and AYAs with cancer (IRB # 2019-0623).

13.3 Participant Payment

Participants will be compensated for the time required for assessment completion. Compensation for survey completion (est. completion time: 30-45 minutes) was set at \$20. Participants will be compensated an additional \$5 weekly, for 17 weeks, for using and downloading data from their electronic adherence monitoring device. If a participant completes all Feedback Group or Tailored Group procedures, they will be compensated a \$15 bonus. Participants will also be compensated an additional \$10 upon return of the study-provided electronic adherence monitoring device at the conclusion of the study (either at study completion or at drop-out – whenever the electronic monitoring device is returned).

Table 6. Incentive Schedule

Task	Amount
Pre-Treatment Assessment	\$20
Weekly eCAP downloads (4 week run-in + 1 week for pre-treatment assessment + 8 weeks of intervention + 4 weeks post-intervention = 17 weeks)	\$5/week (total up to \$85)
Group completion bonus	\$15
Post-Treatment Assessment	\$20
eCAP return	\$10
Max Total = \$150	

In the event that a study phone is not returned, we will attempt to reach the family via phone and email and set up a way to retrieve the phone. Given the high costs of the phones, if, after several months it is still not returned, we will offer an incentive of \$50 for the safe return of the working mobile device, no questions asked. Other BMCP faculty have had success in using this procedure to increase mobile device return rates.

All compensation will be managed by the study team at CCHMC and provided via ClinCards.

14.0 WITHDRAWAL OF SUBJECTS

There are no anticipated circumstances under which subjects will be withdrawn from the research without their consent.

If participants wish to withdraw from the study, they are asked to contact the study team in writing. Following withdrawal, no additional attempts will be made to contact participants and no new data will be collected. Data collected prior to withdrawal, however, will still be analyzed. These procedures are detailed in the consent document.

15.0 RISKS TO SUBJECTS

This is a minimal risk study, including risks no greater than those encountered in routine behavioral assessment and clinical care. There are no medical risks. Participation in all study procedures is voluntary and participants can withdraw at any time.

Risk of Discomfort: Prior to study participation, AYAs will be reminded that they may decline to answer any question that makes them feel uncomfortable. In the unlikely event that the content of a study visit or intervention session causes emotional or psychological distress, the Principal Investigator, [name], a licensed clinical psychologist at CCHMC (or the licensed clinical psychologist providing back-up coverage) will be contacted immediately to assess the situation. The licensed clinical psychologist will follow-up with patient's medical team as necessary. These procedures will also be followed should concerns regarding abuse, self-harm, homicidal/suicidal thoughts or behaviors arise. Patients and caregivers will be made aware that any information obtained during their participation that suggests the potential for harm to self or others will be disclosed to their medical team in order to protect the patient. As study procedures are conducted virtually, patients and families will be instructed to go to the local ED or call 911 if there is an immediate safety concern.

Risk of Loss of Privacy of Data: There is also the risk of possible loss of privacy of data or loss of confidentiality. These risks are inherent in all research studies. While HIPAA-compliant health technology services will be used to remotely access medication adherence data (CertiScan® cloud) and deliver

assessments and intervention sessions (Zoom for Healthcare), there is a risk of loss of privacy of data and a risk of loss of confidentiality associated with health technology use. A statement to this effect will be included in the consent documents. Every effort will be made to ensure that all participant information will be kept confidential and secure (as detailed in Section 17).

Unanticipated problems related to the research will be reported to the IRB within 24 hours of [name] (PI) becoming aware of the problem. Unanticipated problems will also be regularly reported to [name], the Independent Data Safety Monitor for this study.

16.0 POTENTIAL BENEFIT TO SUBJECTS

AYAs randomized to either the treatment (Tailored Program) or control (Feedback Program) arm may benefit from improved medication adherence, which has the potential to improve health outcomes. The information gained will improve our understanding of how best to help AYAs with cancer adhere to their medication regimens. The minimal risks associated with study participation are deemed reasonable in relation to the aforementioned anticipated benefits to participants and others.

17.0 DATA MANAGEMENT AND CONFIDENTIALITY

17.1 Sample Size Justification

A medical record review was conducted to determine the number of eligible AYAs across each site. In 2019, an estimated 97 AYAs ages 15-24 years of age with a diagnosis of cancer prescribed an oral prophylactic or chemotherapy medication (anticipated duration > 17 weeks) received care at one of the three participating sites: Cincinnati Children's Hospital Medical Center (CCHMC), Seattle Children's Hospital, and St. Jude Children's Research Hospital. Of these 97 AYAs, based on enrollment data from our preliminary studies, it is estimated that 5% (n = 5) will be excluded due to lack of English fluency, presence of significant cognitive deficits, poor medical status, and/or participation in a medical clinical trial. In our preliminary studies, 29% of AYAs took \geq 95% of doses and 3% declined to use an electronic monitoring device (total = 32%). Based on these data, we conservatively estimate that an additional 35% will not meet the adherence-related criteria (< 95% adherence during run-in; AYA uses electronic monitoring device without difficulty) and be excluded. Thus, in all, we estimate that 39 of the 97 AYAs will not meet inclusion criteria ($97 * [0.05 + .35] = 39$), resulting in an estimated eligible sample of 58 AYAs ($97 - 39 = 58$).

We have set our recruitment rate goal of 70%, well below our previous enrollment rates of 79-92% into multi-site observational psychosocial studies including AYAs with cancer. Based on an enrollment rate of 70%, it is estimated that we will enroll 3-4 AYAs per month and meet our recruitment goal of N = 40 ($58 * .70 = 40$) in 12 months.

As it is estimated that approximately 58 AYAs with cancer meeting the inclusion criteria will receive care at one of the 3 participating sites during the 12 month recruitment period, a target N of 40 (randomized) was set to test our ability to achieve a 70% recruitment rate ($58 * .70 = 40$). Assuming 20% attrition, our estimated final N will be 32, a number that exceeds the recommended sample size (n = 20) for a pilot 2-arm RCT with the goal of informing an efficacy trial with 80% power to detect a medium effect.³⁶

17.2 Data Analysis Plan

Hypothesis 1a: The intervention will meet enrollment, retention, fidelity, and data completion feasibility criteria.

Hypothesis 1a will be supported if descriptive statistics indicate the feasibility criteria in Table 7 are met. The percent of eligible approached AYAs who enroll will be calculated to explore the hypothesis that the intervention will meet the enrollment rate goal of 70%. The percentage of AYAs completing all study procedures and with complete data will be calculated to evaluate the hypothesis that the retention and

assessment completion rates will be “acceptable”³⁷ as defined as 80% or higher. In addition, the percentage of AYAs who received the intervention length, contact, content, and duration as specified in the treatment protocol will be calculated to evaluate the hypothesis that intervention fidelity will be “high”³⁹ as defined as 80% or higher.

Table 7. Hypothesis 1A Measures

Domain	Measure	Outcome	Criteria
Feasibility (Hyp 1a)	Enrollment Rate	Percentage of eligible approached AYAs who enroll	≥ 70%
	Retention Rate	Percentage of AYAs completing all study procedures	≥ 80% ³⁷
	Assessment Completion	Percentage of AYAs with complete data	≥ 80% ³⁷
	Intervention Fidelity ³⁸	Percentage of AYAs receiving the intervention length, contact, content, and duration as specified in the protocol	≥ 80% ³⁹

Hypothesis 1b: AYAs will rate the intervention as easy to use and acceptable.

Participants in both the treatment and control arms will complete usability and acceptability measures (see Table 8) in an effort to promote blinding. Data from the treatment group will be analyzed separately to explore Hypothesis 1b. Mean System Usability Scale, System Usability Scale Adjective Rating, and Acceptability &Adherence Scale scores will be calculated for AYAs randomized to the treatment group. It is hypothesized that AYAs participating in the treatment group will rate the intervention as easy to use as defined by a mean System Usability Scale score of 68 or greater³⁹ and a mean System Usability Scale Adjective Rating of 4 or higher.⁴¹ It is also hypothesized that AYAs participating in the treatment group will rate the intervention as acceptable as defined by a mean Acceptability &Adherence Scale score of 28 or higher.⁴²

Table 8. Hypothesis 1B Measures

Domain	Measure	Outcome	Criteria
Usability (Hyp 1b)	System Usability Scale (SUS) ⁴⁰	Mean score of AYAs randomized to treatment group	M ≥ 68 ⁴⁰
	System Usability Scale Adjective Rating ⁴¹	Mean score of AYAs randomized to treatment group	M ≥ 4 ⁴¹
Acceptability (Hyp 1b)	Acceptability &Adherence Scale ⁴²	Mean score of AYAs randomized to treatment group	M ≥ 28 ⁴³

Data from the open-ended refinement questions (see Table 2) will be coded in NVivo by two independent raters using theoretical thematic analysis, a method selected as it codes for themes related to specific research questions such as those posed in this grant (i.e., “What could we change about the intervention to make it more acceptable to AYAs?”).

Exploratory Aim 2: To explore group differences in improvements in electronically-monitored medication adherence to inform the next phases of intervention development and testing.

To explore group differences in improvements in electronically-monitored medication adherence to inform the next phases of intervention development and testing (Exploratory Aim 2), we will conduct longitudinal mixed effects models using Stata version 16.⁴⁹ Longitudinal trajectories of adherence will be estimated and tested for treatment group differences.

While this study is not designed to test for treatment-related differences in adherence by demographic or clinical variables, demographic (age, sex, race), clinical (side effects, diagnosis, additional adherence interventions), and psychosocial variables (parental involvement, emotional distress) previously associated with adherence¹⁰ (see Table 3) will be explored as potential covariates. Exploring the role of these variables as covariates will enhance the precision of our efficacy estimate. Data will also be disaggregated by sex in all publications to facilitate efforts to consider sex in the interpretation and generalization of findings.

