4.0 STUDY ENDPOINTS

4.1 Primary and Secondary Study Endpoints

Hypothesis 1A: The primary endpoint for this study is the enrollment rate. Secondary outcomes for Hypothesis 1A include retention rate, assessment completion, and intervention fidelity as detailed in Table 1.

Table 1. Hypothesis 1A Measures

Domain	Measure	Outcome	Criteria
Feasibility (Hyp 1a)	Enrollment Rate	Percentage of eligible approached AYAs who enroll	≥ 70%
	Retention Rate	Percentage of AYAs completing all study procedures	≥ 80% ³⁶
	Assessment Completion	Percentage of AYAs with complete data	≥ 80% ³⁶
	Intervention Fidelity: Contact ³⁷	Percentage of AYAs who received 4 intervention sessions (planned number of sessions)	≥ 80% ³⁸
	Intervention Fidelity: Length ³⁷	Percentage of AYAs whose average session length was between 30 and 45 minutes (planned session duration)	≥ 80% ³⁸
	Intervention Fidelity: Duration ³⁷	Percentage of AYAs who completed the intervention sessions within an 8-10 week timeframe (8 weeks = planned duration; 10 weeks = upper limit set to include a 2 week buffer to provide flexibility for patients who may be hospitalized and/or experience major complications during the intervention period)	≥ 80% ³⁸
	Intervention Fidelity: Content ³⁷	Percentage of AYAs receiving the BCTs matched to their barriers per protocol (assessed via listening to audio recordings of sessions and coding delivered BCTs using a fidelity rating checklist)	≥ 80% ³⁸

Hypothesis 1B: Outcomes for Hypothesis 1B include usability and acceptability as detailed in Table 2. Open-ended questions regarding usability and acceptability will also be asked to inform potential refinements.

Table 2. Hypothesis 1B Measures

Domain	Measure	Outcome	Criteria
Usability (Hyp 1b)	System Usability Scale (SUS) ³⁹	Mean score of AYAs randomized to treatment group	M ≥ 68 ³⁹
	System Usability Scale Adjective Rating ⁴⁰	Mean score of AYAs randomized to treatment group	M ≥ 4 ⁴⁰
Acceptability (Hyp 1b)	Acceptability & Adherence Scale ⁴¹	Mean score of AYAs randomized to treatment group	M ≥ 28 ⁴²
Refinements	3 Open-Ended Questions (1. What did you like best about the program?; 2. What could we change to make the program better?; 3. Anything else we should think about as we work to make this program better?)		N/A

Exploratory Aim 2: The outcome for Exploratory Aim 2 is electronically-monitored medication adherence.

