6.2 Study Procedures

6.2.a. Electronic Monitoring of Medication Adherence. In this study, medication adherence will be monitored using an electronic pill bottle. The electronic pill bottle includes a computer chip in the cap that records a date- and time-stamp of each time the bottle is opened, our proxy for medication-taking behavior.

To be eligible for the study, AYAs must demonstrate < 95% adherence and use the electronic monitor without difficulty. A 4-week run-in period is included to assess these eligibility criteria. After an AYA is enrolled, they will receive an electronic monitoring device and be asked to store their eligible oral medication in this device for the duration of their participation in the study. AYAs who demonstrate ≥ 95% adherence during the 4-week run-in period and/or who have difficulty using the electronic monitoring device will be informed that they do not meet the eligibility criteria and their study participation will be ended at that point. AYAs with < 95% run-in adherence will continue with study procedures per Fig. 3 and be asked to continue to use the electronic adherence monitoring device until the end of the 4-week post-intervention period (for 17 total weeks).

Electronic Monitoring Device Distribution: AYAs will either be provided an electronic monitoring device at their recruitment visit or mailed an electronic monitoring device and provided instructions by a member of the CCHMC research team.

For participants currently enrolled in an ongoing clinical initiative including electronic adherence monitoring, adherence data will be downloaded from the clinic-provided device. Doing so will ensure that participants are only provided with one electronic monitor.

Electronic Monitoring Device Return: Participants will be asked to return their adherence electronic monitoring device at the conclusion of their participation in the study. In instances where participants are unable to bring their adherence electronic monitoring device to a study visit, a pre-paid addressed envelope will be provided so participants can mail their devices to the study team.

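### Do the 80% retention and assessment-completion criteria need a stated denominator and a by-arm rule?

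*Combined protocol and SAP*

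**What the plan says.** Table 1 (section 4.1) and Table 7 (section 17.2) define retention as "Percentage of AYAs completing all study procedures" and assessment completion as the share with complete data. Each has a criterion of at least 80%. The prose of section 17.2 is no more specific: "The percentage of AYAs completing all study procedures and with complete data will be calculated to evaluate the hypothesis" that both rates are high enough. The decision rule is descriptive: "Hypothesis 1a will be supported if descriptive statistics indicate the feasibility criteria in Table 7 are met".

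Other rows do name their population. Enrollment is taken over eligible AYAs who were approached. The Hypothesis 1b measures are each a "Mean score of AYAs randomized to treatment group". The fidelity row of Table 7 again has the bare term: "Percentage of AYAs receiving the intervention length, contact, content, and duration as specified in the protocol".

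Three other places bear on the denominator:

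- Section 17.1, starting from the 40 randomized: "Assuming 20% attrition, our estimated final N will be 32".
- Section 6.2.a, which uses the word enrolled before the run-in: "After an AYA is enrolled, they will receive an electronic monitoring device".
- Section 12.2, under which an estimated 10–20 additional AYAs "will be enrolled until a total of 40 AYAs are randomized".

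**The concern.** Three readings of the denominator seem open: all 40 randomized, all enrolled (50–60), or the Tailored arm alone (20). The last gains some support from the fidelity row, where the same bare term can only mean the arm that has sessions. If the choice were made after the data were seen, the same completers could pass or fail.

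The second worry is masking. Hypothesis 1a speaks of the intervention meeting its criteria, yet a pooled rate lets good retention in the Feedback arm offset poor retention in the Tailored arm. Unequal loss is plausible: Tailored AYAs are asked for four sessions of 30–45 minutes, and Feedback AYAs receive a weekly text. Section 7.1 says the data will inform a larger multi-site trial, for which arm-specific attrition would be useful.

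**Working it through.** **Inputs from the documents.** 40 randomized, 20 per arm (section 2.0); 20% attrition (17.1); 10–20 extra enrolled (12.2), so 50–60 enrolled in total; criterion 80% (Tables 1 and 7).

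**The plan's own figure.** 40 × (1 − 0.20) = 32, as stated in section 17.1. 32/40 = 80.0%, so the planning assumption is the exact complement of the retention criterion.

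**Denominator.**

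| Completers | Denominator | Rate | At least 80%? |
|---|---|---|---|
| 32 | 40 randomized | 80.0% | yes |
| 32 | 50 enrolled | 64.0% | no |
| 32 | 60 enrolled | 53.3% | no |
| 40 | 50 enrolled | 80.0% | just |
| 40 | 60 enrolled | 66.7% | no |

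The last two rows test the all-enrolled reading. If every randomized AYA finished, the rate would still be only 67–80%. AYAs who reach 95% adherence in the run-in, or who have difficulty with the device, are ineligible under criteria 8 and 9, and section 6.2.a ends their participation. They cannot complete all procedures, so a retention measure that counts them as failures would mostly measure run-in eligibility.

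**Tailored arm only.** Section 17.2 says that treatment-group data are analysed separately for Hypothesis 1b and says nothing similar for 1a. The fidelity row is limited to one arm by its content, since only that arm has sessions. Retention and data completion apply to both arms.

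**Masking under the pooled rule.** 14/20 + 18/20 = 32/40 passes; the extreme split is 12/20 + 20/20. With T ~ Bin(20, pT) and F ~ Bin(20, pF) independent, the documents give no arm-specific rates, so all pT and pF below are assumptions.

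| True Tailored / Feedback | P(T + F ≥ 32) | P(T + F ≥ 32 and T < 16) |
|---|---|---|
| 80% / 80% | 0.59 | 0.10 |
| 85% / 85% | 0.86 | 0.09 |
| 90% / 90% | 0.98 | 0.03 |
| 75% / 80% | 0.44 | 0.13 |
| 70% / 80% | 0.30 | 0.13 |
| 75% / 85% | 0.59 | 0.22 |
| 70% / 90% | 0.59 | 0.36 |
| 65% / 95% | 0.59 | 0.48 |

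The last three rows hold the mean at 80%, with Feedback exactly offsetting the Tailored shortfall. Where it does not offset, the pooled rule itself passes less often.

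**Effect of the fidelity criterion.** Hypothesis 1a also needs 80% fidelity in the Tailored arm (16/20). Assume losses spread evenly over the 8 session weeks and the 4 weeks after, and let q be the share of those reaching session 4 who meet the remaining fidelity elements. The probability that both criteria pass with T < 16 is:

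| Tailored / Feedback | q = 1 | q = 0.95 | q = 0.90 |
|---|---|---|---|
| 75% / 85% | 0.17 | 0.11 | 0.07 |
| 70% / 90% | 0.25 | 0.17 | 0.10 |
| 65% / 95% | 0.28 | 0.18 | 0.11 |

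With q = 1 it is 0 if all losses fall during the sessions, and returns to 0.22, 0.36 and 0.48 if all fall afterwards.

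**Precision.** Exact 95% intervals: 32/40, 64–91%; 16/20, 56–94%; 14/20, 46–88%. The interval for 14/20 contains 80%, so an arm-level shortfall of that size would not establish that Tailored retention is below the criterion.

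**The case for a change.** The strongest case for a change is that the protocol itself creates the ambiguity. It uses enrolled for a stage before the run-in in section 6.2.a but for reaching the 40 randomized in section 17.1. Section 12.2 mentions AYAs who miss the pre-treatment visit and are replaced, and it describes them as not completing procedures, in terms close to the retention measure. Fixing the denominator costs one word and is worth most before results are known. Fidelity does not cover losses in the four weeks after the last session.

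Part of this stands. The tables do not say randomized, and adding the word would be sensible editing. AYAs lost between consent and randomization belong in the participant flow, by reason, and the pooled rate alone does not support a statement about retention on the Tailored program.

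The rest does not lead to a different rule. Making the Tailored rate a second gate would be harsh at n = 20: with a true 80%, the arm falls below 16/20 with probability 0.37. With a true 85% in both arms, the chance of passing would drop from 0.86 to 0.78. Requiring a lower confidence limit of 80% would need 38/40 overall or 20/20 in one arm. If the pooled criterion is kept, as it reasonably should be, 14/20 + 18/20 still passes, so the clarification would not remove the case that prompted the worry.

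**Conclusion.** No change is needed. The omission is real but is one that analysts fill sensibly: Aim 1, the attrition sentence in section 17.1 and the separate-arm statement confined to Hypothesis 1b all point to the 40 randomized. On that denominator, 32/40 meets the criterion as planned. The 64% and 53% figures depend on an all-enrolled reading under which perfect retention would score only 67–80%.

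Pooling is a fair trade-off for a pilot whose first aim is to show that the RCT can be run. A pooled pass with the Tailored arm observed below 16/20 has probability 0.03–0.10 if both arms truly retain 80–90%. It reaches 0.22–0.48 only under assumed arm differences of 10 to 30 points with exact offsetting, and before the fidelity criterion is applied. These are secondary, descriptive outcomes with no progression rule attached, and counts by arm with exact intervals can be reported from the same data at any time. The conclusion rests on reading the bare term as randomized AYAs, which the documents imply but do not state.
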